PROTOCOL TITLE: The Effect of an Electronic Medical Record (EMR) Alert on Hepatitis B Screening: A Randomized Controlled Trial.

Patients will be identified as previously aforementioned. The only identifying information will be patient MRNs. There will be minimal risks for those identified who meet inclusion criteria. We will be activating the alert system-wide in a great number of patients. For these reasons, obtaining HIPAA authorization from subjects would not be feasible. Appropriate precautions will be taken to ensure that the privacy rights of those identified will be maintained.

9) Compensation to the Subjects

Patients will not be compensated.

10) Study Timelines

We anticipate that we will be able to recruit all 14,000 subjects for the study within 12 months. Once the EMR alert is released to a patient's chart, we will perform quarterly EMR data searches to determine if the primary care physician has ordered the HBsAg on those patients. Once a HBsAg test is ordered, the result will be recorded and the patient's participation in the study will end. If no HBsAg test is ordered, we will continue our quarterly EMR data searches to determine if the primary care physician orders the HBsAg at subsequent visits. The post-EMR release observation period may last up to 2 years. If no HBsAg test is ordered at the end of 2 year observation, the patient's participation in the study will end. The study will end on October 31, 2024 due to additional participants to allow time for data collection, analysis, and manuscript writing.

11) Study Endpoints

The study end points will be measurement of an HBsAg level after the EMR alert is release to each patients chart. As mentioned, certain proportion of patients will not reach this end point and this will be recorded.

12) Procedures Involved

- A list of patients meeting the eligibility requirements stated above will be obtained by searching the UC Davis EMR. At a given time, computerized 1:1 randomization of these patients will occur placing them in the intervention or control group. After randomization, the EMR alert will be released in the patients' charts notifying primary care doctors that these patients should be screened for hepatitis B with a HBsAg test. Control group patients will not have the EMR alert released in their chart and will undergo "usual care." As mentioned above (see Study Timelines), we will perform quarterly

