PROTOCOL TITLE: The Effect of an Electronic Medical Record (EMR) Alert on Hepatitis B Screening: A Randomized Controlled Trial.

EMR searches to determine if a HBsAg test was ordered by the patient's primary care physician in response to the EMR alert. We will continue to perform quarterly EMR searches to determine if HBsAg tests are ordered at subsequent visits up to 2 years after the index visit.

- The data points that will be collected are MRN, age, sex, number of office visits, primary language, insurance type (private, medi-cal, or medicare), hepatitis B antigen test result, and date of the hepatitis B antigen test. All data points will strip off identifiable information. Study ID will be assigned and codes created are the only links to identifiable information.
- Patients who are randomly chosen for this study will be number coded. The only link to the patient identifiers will be through a separate key code which will be kept on a secure, password-protected computer. Any paper copies of such information will be kept in a locked filing cabinet in the division office accessible only to the PI and co-PI. The key code will be destroyed once it is confirmed that the data collection is complete.

13) Data and/or Specimen Management and Confidentiality

Will data be banked for future use?

Yes No

If yes, will the data that are banked be identifiable?

Yes, the data will be identifiable:
 No, the data will be completely anonymous.

No, the data will be stripped of identifiers and coded. The link to the individual's identity will not be accessible by the research team.

Where will the data be stored?

How long will the data be stored?

Who will have access to the data?

Describe the procedures to release data, including: the process to request a release, approvals required for release, who can obtain data or specimens, and the data to be provided with specimens.

PROTOCOL TITLE: The Effect of an Electronic Medical Record (EMR) Alert on Hepatitis B Screening: A Randomized Controlled Trial.

- 14) Data and/or Specimen Banking:** Not applicable.
- 15) Provisions to Monitor the Data to Ensure the Safety of Subjects:**
All data will be stored in a password protected Excel file on a secure server and uploaded to REDCap, which is a secure web application, used to build and manage online databases specifically for research, supported by the CTSC. Only those directly involved in research design, data gathering analysis will have access to the database.

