- 16) Withdrawal of Subjects:** A patient will be withdrawn from the study by our staff if they fail to make at least one clinic appointment after release of EMR alert during the observation period. This may be due to change or insurance, being lost to follow up, or death.
- 17) Risks to Subjects**
This record/data review poses the risk of loss of confidentiality. This risk will be minimized by coding of patients' data and protection of private health information. This study will abide by all regulations in place governing the protection of human subjects and protected health information.
- 18) Potential Benefits to Subjects**
The direct benefit to subjects is that they may have an increased chance of screening for hepatitis B since the EMR alert will be reminding their primary care doctors to do so.
- 19) Vulnerable Populations:** Not applicable.
- 20) Multi-Site Research:** Not applicable.
- 21) Community-Based Participatory Research:** Not applicable.
- 22) Sharing of Results with Subjects**
The results will not be shared with the subjects.
- 23) Setting:** This project will be conducted solely among UC Davis primary care network clinic sites.
- 24) Resources Available**

[name], MPH is an Assistant Professor of Internal Medicine in the Division of Gastroenterology and Hepatology. He is primarily interested in

PROTOCOL TITLE: The Effect of an Electronic Medical Record (EMR) Alert on Hepatitis B Screening: A Randomized Controlled Trial.

outcomes research in viral hepatitis resulting in several first author publications in the field. Since coming to UC Davis, he has been involved in several projects including SCrATCH B and the R21 Biologic Basis of Disparities in Liver Cancer Survival Among Asian Americans Study. He will be the Principal Investigator of this Study and coordinate the randomization of subjects, EMR data searches, and statistical analysis.

[name] is a Professor, Division of Gastroenterology and Hepatology, Department of Internal Medicine, UC Davis School of Medicine and the Fellowship Director supervising the training of gastroenterologists and hepatologists at UC Davis. [name] serves as the primary hepatologist treating patients with hepatitis B in the UC Davis Health System. He is the Principle Investigator for SCrATCH B and the R21 Biologic Basis of Disparities in Liver Cancer Survival Among Asian Americans Study and will serve as a mentor to [name] during this study.

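### Withdrawal, endpoint and follow-up are timed from alert release, which controls never have; with no control start date or denominator stated, the comparison could drop patients from one arm only, or cover attenders only

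*Combined protocol and SAP*

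**What the plan says.** - **Section 16 (Withdrawal of Subjects):** a patient is "withdrawn from the study by our staff if they fail to make at least one clinic appointment after release of EMR alert"; attendance is judged over the whole of follow-up. Change of insurance, loss to follow-up and death are given as possible reasons.
- **Section 12 (Procedures Involved):** "Control group patients will not have the EMR alert released in their chart". Randomisation is 1:1 and the alert is released afterwards.
- **Section 10 (Study Timelines):** quarterly searches begin once the alert is in the chart, and "The post-EMR release observation period may last up to 2 years".
- **Section 11 (Study Endpoints):** the endpoint is "measurement of an HBsAg level after the EMR alert is release to each patients chart". It adds that a "certain proportion of patients will not reach this end point and this will be recorded".
- **Section 12 again:** the searches look for tests ordered by the patient's "primary care physician in response to the EMR alert", and run "up to 2 years after the index visit". That visit is not defined for either arm.

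No available section names a start date for controls, an analysis population, or how withdrawn patients are counted. The material between Sections 24 and 29 was not available for this review, so this statement covers only the rest.

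**The concern.** The endpoint, the observation period and the withdrawal rule all depend on an event that occurs in one arm only. Read strictly, a control patient could never reach the endpoint, so some other start date must be intended for controls. None is written. The undefined index visit is a second clock, so the start is unclear even in the alert arm.

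Withdrawal matters most. Not attending occurs after randomisation and is closely tied to the outcome, because a patient with no visit has little opportunity to be tested. If withdrawn patients leave the denominator, two readings remain:

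1. **One-arm reading.** The rule operates only where an alert exists. Rarely tested patients leave the intervention arm and stay in the control arm, so the intervention rate rises even if the alert does nothing.
2. **Both-arms reading.** The rule applies to everyone from a common date. This creates no false difference provided the alert does not affect attendance, but the result is an effect among attenders, which the protocol does not state.

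Whoever extracts the data has to choose a control start date and a denominator, and the choice changes the result.

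**Working it through.** **Inputs from the protocol (Section 7).** Expected testing is 50% with the alert and 20% in controls; 80% power; two-sided 0.05; 45 per group; planned enrolment 2,000 + 5,000 = 7,000 per arm.

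**Assumed inputs.** The no-visit share m is not in the documents; 1%, 2%, 5% and 10% are shown. The testing rate q among non-visitors is set to 0 or 5%. The test is taken to be a two-sided two-proportion z test. Withdrawn patients are taken to leave the denominator.

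**The plan's own figure.** Without continuity correction, n = [1.96·√(2·0.35·0.65) + 0.8416·√(0.5·0.5 + 0.2·0.8)]² / 0.3² = 38.5. With correction, (38.5/4)·[1 + √(1 + 4/(38.5·0.3))]² = 44.9, so 45 per group. The stated sample size reproduces and is not at fault.

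**One-arm reading, no alert effect.** With overall testing p = 0.20 in both arms, the retained intervention rate is (p − m·q)/(1 − m) on n(1 − m) patients. The control rate stays at p on n patients.

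Example with m = 0.10, q = 0, n = 7,000:
- Intervention: 0.20/0.90 = 0.2222 on 6,300. Control: 0.2000 on 7,000. Difference: 0.0222.
- Pooled rate 2,800/13,300 = 0.2105, so the standard error under the null is √[0.2105·0.7895·(1/6,300 + 1/7,000)] = 0.00708. The unpooled standard error is 0.00709.
- Rejection probability = Φ[(0.0222 − 1.96·0.00708)/0.00709] = Φ(1.18) = 0.88. The opposite tail is negligible.

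| m | q | Spurious difference (points) | False positives, 7,000 per arm | 2,000 per arm | 45 per arm |
|---|---|---|---|---|---|
| 1% | 0 | 0.20 | 6% | 5% | 5% |
| 2% | 0 | 0.41 | 9% | 6% | 5% |
| 5% | 0 | 1.05 | 33% | 13% | 5% |
| 10% | 0 | 2.22 | 88% | 39% | 6% |
| 1% | 5% | 0.15 | 6% | 5% | 5% |
| 2% | 5% | 0.31 | 7% | 6% | 5% |
| 5% | 5% | 0.79 | 21% | 9% | 5% |
| 10% | 5% | 1.67 | 66% | 24% | 5% |

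Simulation with 40,000 runs at 7,000 per arm agrees for m = 5% and 10%. Under the both-arms reading, and with all randomised patients analysed, the simulated false-positive rate is about 5%.

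**Planned effect, m = 0.10.** The true difference over all randomised patients is 30 points.
- One-arm reading: (0.50 − 0.10·q)/0.90 − 0.20 = 35.6 points (q = 0) or 35.0 points (q = 5%).
- Both-arms reading: (0.50 − 0.20)/0.90 = 33.3 points.

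**The case against.** The one-arm reading needs two steps that nobody wrote down: that release is a per-patient event controls cannot have, and that withdrawal means leaving the denominator.

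On the first step, the rule is worded for any patient, and its listed reasons apply equally to both arms. Randomisation takes place at a set time with release afterwards, and Section 8 speaks of activating the alert across the system, so release could be a calendar date usable for everyone. Against this, Sections 10 and 11 describe release to the individual patient's chart, and no section gives controls that date.

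On the second step, Section 10 also ends participation for tested patients and for those untested at 2 years, and both groups plainly still count; Section 16 may be equally administrative. Section 7 states its expected rates as proportions of each group with no attendance condition, and Section 11 says that patients without the endpoint are recorded. Both lean towards keeping everyone, but neither says how withdrawn patients count.

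The no-visit share is assumed, and the false-positive figures depend heavily on it. They also assume no alert effect. An effect among attenders is a legitimate target if it is specified.

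These points make the both-arms and all-randomised readings plausible. They do not supply the missing start date or denominator.

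**Conclusion.** The concern holds. The sections conflict: the rules are anchored to an event that one arm never has, and Section 16 states a post-randomisation removal rule that, taken literally, can operate only in the alert arm.

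Under that literal reading the spurious difference is modest, about 1 to 2 points at an assumed no-visit share of 5% to 10%. The enlarged sample of 7,000 per arm makes a difference of that size significant in 21% to 88% of trials with no effect; at a share of 1% to 2% the figure is 6% to 9%. These figures are illustrative and rest on withdrawn patients leaving the denominator.

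Under the both-arms reading there is no null bias if attendance is unaffected, only an unstated restriction to attenders. If all randomised patients are kept from a common date, neither problem arises. If the true effect is near the planned 50% vs 20%, the conclusion of benefit does not change, although its size may be overstated. The exposure is greatest when the true effect is small or nil. This should be fixed before data extraction; confidence is medium, because the text does not show which reading is intended.

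**What to change.** Use the randomisation date as the index date for both arms in Sections 10, 11, 12 and 16, replacing both alert release and the index visit. Suggested text:

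> The endpoint is an HBsAg test dated within 2 years of randomisation. Quarterly EMR searches are run identically in both arms. All randomised patients are analysed in their assigned arm; a patient with no HBsAg test within 2 years of randomisation, for any reason, counts as not tested.

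Keep an analysis of patients with at least one visit as secondary, with visits counted from randomisation and the rule identical in both arms. The common date removes the one-arm problem. Making all randomised patients primary is a further choice, which removes the restriction to attenders.

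Two details should be settled in the same edit. Section 10 allows follow-up of up to 2 years, so state how any shorter follow-up is handled, alike in both arms. Section 10 also tracks orders while Section 11 refers to measurement, so state which one counts.

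**Cost.** The primary analysis needs changes of wording and no new data: the HBsAg test date is already collected (Section 12) and the randomisation date is known. The secondary analysis needs dated visits, because Section 12 lists only a visit count. Testing rates over all randomised patients will look lower than rates among attenders. If release lags randomisation, tests in the gap dilute the difference slightly.

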29) Process to Document Consent in Writing: Not applicable.

30) Drugs or Devices: Not applicable.
